5.6.3 Documentation of Prior and Concomitant Medication Use

All concomitant medications must be recorded in the eCRF. Any medication taken on or after the date the patient signs informed consent will be recorded in the eCRF. Any changes to concomitant medication dosing during the study will be captured in the eCRF and closely monitored.

6 STUDY PROCEDURES

Blood sample collection will be prioritized starting with the safety sample.

All blood samples should be collected while the patient is in a fasted state, defined as nothing by mouth except water for ≥ 6 hours.

A ± 3 -day window is acceptable for all visits during the Treatment Period, except for Days 1 and 14 in Part A, when the window is ± 1 day.

6.1 Informed Consent

Written informed consent for the study will be obtained from all patients before any protocol-specific procedures are performed.

6.2 Screening Period (Parts A and B) (Weeks -12 to -1)

The following procedures will be performed during the Screening Period (Weeks -12 to -1):

- Obtain informed consent.
- Evaluate inclusion/exclusion criteria.
- Obtain demographics and medical history.
- Record prior and concomitant medications.
- Perform complete physical examination.
- Measure height and body weight and calculate BMI.
- Measure waist circumference (Part A only).
- Measure waist and hip circumferences (Part B only).
- Calculate waist to hip ratio (WHR) and waist to height ratio (WHtR) (Part B only).
- Collect vital signs (systolic and diastolic blood pressure, heart rate, respiratory rate, and body temperature) with the patient in the sitting position after 5 minutes of rest and before any blood draws.
- Administer the AUDIT-C test. Patients with AUDIT-C scores ≥ 3 points at screening will receive the full AUDIT and will be excluded if they score ≥ 8 points on the full AUDIT. Patients with AUDIT-C scores < 3 points will not receive the full AUDIT.
- Counsel on diet/lifestyle.
- Collect blood sample for the following:
 - Anti-HCV, anti-HIV, and anti-HBV status and HCV RNA reflexive testing, except if viral serology data are already available in the patient's medical history/records and obtained within 90 days prior to screening.
 - Chemistry, hematology, coagulation, and lipid and metabolic profile.
 - Serum pregnancy test (only for women of childbearing potential).

- Follicle-stimulating hormone test (only for women ≤ 55 years of age, to confirm postmenopausal state).
- Plasma storage.
- Collect urine sample for urinalysis.
- Perform 12-lead ECG.
- Perform FibroScan.
- Perform MRI-PDFF and cT1 imaging if FibroScan values (liver stiffness measurement [LSM] and CAP) are within eligibility range.
- Assess adverse events.

6.3 Treatment Period (Weeks 0 to 12)

6.3.1 Part A: Safety Run-in Period (Weeks 0 to 4)

6.3.1.1 Day 1 (Week 0)

The following procedures will be performed on Day 1 (Week 0):

- Review inclusion/exclusion criteria and confirm patient eligibility.
- Record changes in concomitant medications.
- Perform brief physical examination.
- Measure body weight and calculate BMI.
- Measure waist circumference.
- Collect vital signs (systolic and diastolic blood pressure, heart rate, respiratory rate, and body temperature) with the patient in the sitting position after 5 minutes of rest and before any blood draws.
- Counsel on diet/lifestyle.
- Collect blood sample for the following:
 - Chemistry, hematology, coagulation, and lipid and metabolic profile.
 - Intense PD profile (predose [fasting] and 4 [fasting], 6, 10, 12, and 24 hours postdose).
 - Liver fibrosis and inflammation.
 - Intense PK profile (predose and 1, 2, 4, 6, 8, 10, 12, and 24 hours postdose [samples will be collected in the fasted state predose to 4 hours postdose, inclusive]).
- Collect urine sample for urinalysis and pregnancy test. If the pregnancy test is positive, perform serum hCG test.
- Randomize eligible patients prior to dosing.
- Assess pruritus.
- Assess adverse events.

- Dispense patient diary.
- Dispense study drug and provide dosing instructions.

6.3.1.2 Day 7 (Week 1)

The following procedures will be performed on Day 7 (Week 1):

- Record changes in concomitant medications.
- Perform brief physical examination.
- Measure body weight and calculate BMI.
- Measure waist circumference.
- Collect vital signs (systolic and diastolic blood pressure, heart rate, respiratory rate, and body temperature) with the patient in the sitting position after 5 minutes of rest and before any blood draws.
- Counsel on diet/lifestyle.
- Collect blood sample for the following:
 - Chemistry, hematology, coagulation, and lipid and metabolic profile.
 - Liver fibrosis and inflammation.
 - Sparse PK profile (predose [fasting] and 2 hours postdose; optional sample at 6 hours postdose).
- Collect urine sample for urinalysis and pregnancy test. If the pregnancy test is positive, perform serum hCG test.
- Perform 12-lead ECG.
- Assess pruritus.
- Assess adverse events.

6.3.1.3 Day 14 (Week 2)

The following procedures will be performed on Day 14 (Week 2):

- Record changes in concomitant medications.
- Perform brief physical examination.
- Measure body weight and calculate BMI.
- Measure waist circumference.
- Collect vital signs (systolic and diastolic blood pressure, heart rate, respiratory rate, and body temperature) with the patient in the sitting position after 5 minutes of rest and before any blood draws.
- Administer the AUDIT-C test.
- Counsel on diet/lifestyle.

- Collect blood sample for the following:
 - Chemistry, hematology, coagulation, and lipid and metabolic profile.
 - Intense PD profile (predose [fasting] and 4 [fasting], 6, 10, 12, and 24 hours postdose).
 - Intense PK profile (predose and 1, 2, 4, 6, 8, 10, 12, and 24 hours postdose [samples will be collected in the fasted state predose to 4 hours postdose, inclusive]).
- Collect urine sample for urinalysis and pregnancy test. If the pregnancy test is positive, perform serum hCG test.
- Perform 12-lead ECG.
- Assess pruritus.
- Assess adverse events.
- Collect returned used/unused study drug and assess compliance.
- Dispense new study drug and provide dosing instructions.

6.3.1.4 Day 21 (Week 3)

The following procedures will be performed at Day 21 (Week 3):

- Record changes in concomitant medications.
- Perform brief physical examination.
- Measure body weight and calculate BMI.
- Measure waist circumference.
- Collect vital signs (systolic and diastolic blood pressure, heart rate, respiratory rate, and body temperature) with the patient in the sitting position after 5 minutes of rest and before any blood draws.
- Administer the AUDIT-C test.
- Counsel on diet/lifestyle.
- Collect blood sample for the following:
 - Chemistry, hematology, coagulation, and lipid and metabolic profile.
 - Liver fibrosis and inflammation.
 - Sparse PK (predose [fasting] and 2 hours postdose; optional sample at 6 hours postdose).
- Collect urine sample for urinalysis and pregnancy test. If the pregnancy test is positive, perform serum hCG test.
- Perform 12-lead ECG.
- Assess pruritus.
- Assess adverse events.

6.3.1.5 Day 28 (Week 4)

The following procedures will be performed at Day 28 (Week 4):

- Record changes in concomitant medications.
- Perform brief physical examination.
- Measure body weight and calculate BMI.
- Measure waist circumference.
- Collect vital signs (systolic and diastolic blood pressure, heart rate, respiratory rate, and body temperature) with the patient in the sitting position after 5 minutes of rest and before any blood draws.
- Administer the AUDIT-C test.
- Counsel on diet/lifestyle.
- Collect blood sample for the following:
 - Chemistry, hematology, coagulation, and lipid and metabolic profile.
 - Sparse PD profile (predose [fasting] and 2 hours postdose).
 - Liver fibrosis and inflammation.
 - Sparse PK profile (predose [fasting] and 2 hours postdose; optional sample at 6 hours postdose).
- Collect urine sample for urinalysis and pregnancy test. If the pregnancy test is positive, perform serum hCG test.
- Perform 12-lead ECG.
- Assess pruritus.
- Assess adverse events.
- Collect returned used/unused study drug and assess compliance.
- Dispense new study drug and provide dosing instructions.

6.3.2 Part A: Continued Treatment Period (Weeks 5 to 12)

6.3.2.1 Day 56 (Week 8)

The following procedures will be performed on Day 56 (Week 8):

- Record changes in concomitant medications.
- Perform brief physical examination.
- Measure body weight and calculate BMI.
- Measure waist circumference.

- Collect vital signs (systolic and diastolic blood pressure, heart rate, respiratory rate, and body temperature) with the patient in the sitting position after 5 minutes of rest and before any blood draws.
- Administer the AUDIT-C test.
- Counsel on diet/lifestyle.
- Collect blood sample for the following:
 - Chemistry, hematology, coagulation, and lipid and metabolic profile.
 - Sparse PD profile (predose [fasting] and 2 hours postdose).
 - Liver fibrosis and inflammation.
 - Sparse PK profile (predose [fasting] and 2 hours postdose; optional sample at 6 hours postdose).
 - Plasma storage.
- Collect urine sample for urinalysis and pregnancy test. If the pregnancy test is positive, perform serum hCG test.
- Perform 12-lead ECG.
- Assess pruritus.
- Assess adverse events.
- Collect returned used/unused study drug and assess compliance.
- Dispense new study drug and provide dosing instructions.

6.3.2.2 Day 84 (Week 12)

The following procedures will be performed on Day 84 (Week 12):

- Record changes in concomitant medications.
- Perform brief physical examination.
- Measure body weight and calculate BMI.
- Measure waist circumference.
- Collect vital signs (systolic and diastolic blood pressure, heart rate, respiratory rate, and body temperature) with the patient in the sitting position after 5 minutes of rest and before any blood draws.
- Administer the AUDIT-C test.
- Counsel on diet/lifestyle.
- Collect blood sample for the following:
 - Chemistry, hematology, coagulation, and lipid and metabolic profile.
 - Sparse PD profile (predose [fasting] and 2 hours postdose).

- Sparse PK profile (predose [fasting] and 2 hours postdose; optional sample at 6 hours postdose).
- Plasma storage.
- Collect urine sample for urinalysis and pregnancy test. If the pregnancy test is positive, perform serum hCG test.
- Perform 12-lead ECG.
- Perform MRI-PDFF and cT1 imaging.
- Perform FibroScan vibration-controlled transient elastography (VCTE) (optional).
- Assess pruritus.
- Assess adverse events.
- Collect returned used/unused study drug and assess compliance.

6.3.3 Part B: Treatment Period (Weeks 0 to 12)

6.3.3.1 Day 1 (Week 0)

The following procedures will be performed at Day 1 (Week 0):

- Review inclusion/exclusion criteria and confirm patient eligibility.
- Record changes in concomitant medications.
- Perform brief physical examination.
- Measure body weight and calculate BMI.
- Measure waist and hip circumferences.
- Calculate WHR and WHtR.
- Collect vital signs (systolic and diastolic blood pressure, heart rate, respiratory rate, and body temperature) with the patient in the sitting position after 5 minutes of rest and before any blood draws.
- Counsel on diet/lifestyle.
- Collect blood sample for the following:
 - Chemistry, hematology, coagulation, and lipid and metabolic profile.
 - Sparse PD (predose [fasting]).
 - Liver fibrosis and inflammation.
 - Sparse PK (predose [fasting]).
 - Plasma storage.
- Collect urine sample for urinalysis and pregnancy test. If the pregnancy test is positive, perform serum hCG test.
- Randomize eligible patients prior to dosing.

- Assess adverse events.
- Dispense study drug and provide dosing instructions.

6.3.3.2 Day 14 (Week 2)

The following procedures will be performed at Day 14 (Week 2):

- Record changes in concomitant medications.
- Perform brief physical examination.
- Measure body weight and calculate BMI.
- Measure waist and hip circumferences.
- Calculate WHR and WHtR.
- Collect vital signs (systolic and diastolic blood pressure, heart rate, respiratory rate, and body temperature) with the patient in the sitting position after 5 minutes of rest and before any blood draws.
- Counsel on diet/lifestyle.
- Collect blood sample for the following:
 - Chemistry, hematology, coagulation, and lipid and metabolic profile.
 - Sparse PD (predose [fasting]).
 - Sparse PK (predose [fasting]).
 - Plasma storage.
- Collect urine sample for urinalysis and pregnancy test. If the pregnancy test is positive, perform serum hCG test.
- Perform 12-lead ECG.
- Assess adverse events.
- Collect returned used/unused study drug and assess compliance.
- Dispense new study drug and provide dosing instructions.

6.3.3.3 Day 28 (Week 4)

The following procedures will be performed at Day 28 (Week 4):

- Record changes in concomitant medications.
- Perform brief physical examination.
- Measure body weight and calculate BMI.
- Measure waist and hip circumferences.
- Calculate WHR and WHtR.

- Collect vital signs (systolic and diastolic blood pressure, heart rate, respiratory rate, and body temperature) with the patient in the sitting position after 5 minutes of rest and before any blood draws.
- Administer the AUDIT-C test.
- Counsel on diet/lifestyle.
- Collect blood sample for the following:
 - Chemistry, hematology, coagulation, and lipid and metabolic profile.
 - Sparse PD (predose [fasting]).
 - Liver fibrosis and inflammation.
 - Sparse PK (predose [fasting]).
 - Plasma storage.
- Collect urine sample for urinalysis and pregnancy test. If the pregnancy test is positive, perform serum hCG test.
- Perform 12-lead ECG.
- Assess adverse events.
- Collect returned used/unused study drug and assess compliance.
- Dispense new study drug and provide dosing instructions.

6.3.3.4 Day 42 (Week 6)

The following procedures will be performed at Day 42 (Week 6):

- Record changes in concomitant medications.
- Collect blood sample for the following:
 - Chemistry for assessment of ALT, AST, ALP, GGT, and total bilirubin.
- Assess adverse events.
- Collect returned used/unused study drug and assess compliance.
- Dispense new study drug and provide dosing instructions.

6.3.3.5 Day 56 (Week 8)

The following procedures will be performed at Day 56 (Week 8):

- Record changes in concomitant medications.
- Perform brief physical examination.
- Measure body weight and calculate BMI.
- Measure waist and hip circumferences.
- Calculate WHR and WHtR.

- Collect vital signs (systolic and diastolic blood pressure, heart rate, respiratory rate, and body temperature) with the patient in the sitting position after 5 minutes of rest and before any blood draws.
- Administer the AUDIT-C test.
- Counsel on diet/lifestyle.
- Collect blood sample for the following:
 - Chemistry, hematology, coagulation, and lipid and metabolic profile.
 - Sparse PD (predose [fasting]).
 - Liver fibrosis and inflammation.
 - Sparse PK (predose [fasting]).
 - Plasma storage.
- Collect urine sample for urinalysis and pregnancy test. If the pregnancy test is positive, perform serum hCG test.
- Perform 12-lead ECG.
- Assess adverse events.
- Collect returned used/unused study drug and assess compliance.
- Dispense new study drug and provide dosing instructions.

6.3.3.6 Day 70 (Week 10)

The following procedures will be performed at Day 70 (Week 10):

- Record changes in concomitant medications.
- Collect blood sample for the following:
 - Chemistry for assessment of ALT, AST, ALP, GGT, and total bilirubin.
- Assess adverse events.
- Collect returned used/unused study drug and assess compliance.
- Dispense new study drug and provide dosing instructions.

6.3.3.7 Day 84 (Week 12)

The following procedures will be performed at Day 84 (Week 12):

- Record changes in concomitant medications.
- Perform brief physical examination.
- Measure body weight and calculate BMI.
- Measure waist and hip circumferences.
- Calculate WHR and WHtR.

- Collect vital signs (systolic and diastolic blood pressure, heart rate, respiratory rate, and body temperature) with the patient in the sitting position after 5 minutes of rest and before any blood draws.
- Administer the AUDIT-C test.
- Counsel on diet/lifestyle.
- Collect blood sample for the following:
 - Chemistry, hematology, coagulation, and lipid and metabolic profile.
 - Sparse PD (predose [fasting]).
 - Sparse PK (predose [fasting]).
 - Plasma storage.
- Collect urine sample for urinalysis and pregnancy test. If the pregnancy test is positive, perform serum hCG test.
- Perform 12-lead ECG.
- Perform MRI-PDFF and cT1 imaging.
- Perform FibroScan VCTE (optional).
- Assess adverse events.
- Collect returned used/unused study drug and assess compliance.

6.4 End of Study Follow-Up Visit (Parts A and B) (Week 14)

The following procedures will be performed at the EOS Follow-up Visit at Day 98 (Week 14):

- Record changes in concomitant medications.
- Perform brief physical examination.
- Measure body weight and calculate BMI.
- Measure waist circumference (Part A only).
- Measure waist and hip circumferences (Part B only).
- Calculate WHR and WHtR (Part B only).
- Collect vital signs (systolic and diastolic blood pressure, heart rate, respiratory rate, and body temperature) with the patient in the sitting position after 5 minutes of rest and before any blood draws.
- Counsel on diet/lifestyle.
- Collect blood sample for the following:
 - Chemistry, hematology, coagulation, and lipid and metabolic profile.
 - PD.
 - Serum pregnancy test.

- Liver fibrosis and inflammation.
- PK.
- Plasma storage.
- Collect urine sample for urinalysis.
- Perform 12-lead ECG.
- Assess pruritus (Part A only).
- Assess adverse events.

6.5 Early Termination Visit and Withdrawal Procedures (Parts A and B)

The end of treatment for patients completing the study is Day 84 (Week 12).

Patients who discontinue early from the study for any reason before completion of the Treatment Period will be requested to return to the clinic for an ET Visit within a maximum of 48 hours after their last intake of study drug, regardless of how many days they participated in the study.

Patients who discontinue early from the study for any reason after completion of the Treatment Period and before the EOS Follow-up Visit will be requested to return to the clinic for an ET Visit as soon as possible and no later than the planned EOS Follow-up Visit.

For patients who are withdrawn from the study prior to completion, all ET procedures will be performed at an ET Visit. These procedures include the following:

- Record changes in concomitant medications.
- Perform brief physical examination.
- Measure body weight and calculate BMI.
- Measure waist circumference (Part A only).
- Measure waist and hip circumferences (Part B only).
- Calculate WHR and WHtR (Part B only).
- Collect vital signs (systolic and diastolic blood pressure, heart rate, respiratory rate, and body temperature) with the patient in the sitting position after 5 minutes of rest and before any blood draws.
- Administer the AUDIT-C test.
- Counsel on diet/lifestyle.
- Collect blood sample for the following:
 - Chemistry, hematology, coagulation, and lipid and metabolic profile.
 - PD (preferably within 24 to 48 hours of last intake of study drug).
 - Liver fibrosis and inflammation.
 - Serum pregnancy test.

- PK (preferably within 24 to 48 hours of last intake of study drug).
- Plasma storage.
- Collect urine sample for urinalysis.
- Perform 12-lead ECG.
- Perform MRI-PDFF and cT1 imaging only for patients on study drug ≥ 4 weeks.
- Perform FibroScan VCTE (optional).
- Assess pruritus (Part A only).
- Assess adverse events.
- Collect returned used/unused study drug and assess compliance.

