4.4 Withdrawal Criteria

Participation of a patient in this clinical study may be discontinued for any of the following reasons:

- Patient withdrawal of consent or request of discontinuation from the study for any reason
- Occurrence of any medical condition or circumstance that exposes the patient to substantial risk and/or does not allow the patient to adhere to the requirements of the protocol
- Patient meeting any of the stopping rules
- Any SAE, clinically significant adverse event, severe laboratory abnormality, intercurrent illness, or other medical condition which indicates to the Investigator that continued participation is not in the best interest of the patient
- Pregnancy
- Requirement of prohibited concomitant medication
- Patient failure to comply with protocol requirements or study-related procedures
- Termination of the study by the Sponsor or the regulatory authority

If a patient withdraws prematurely from the study due to the above criteria or any other reason, study staff should make every effort to complete the full panel of assessments scheduled for the ET Visit. The reason for patient withdrawal must be documented in the electronic case report form (eCRF).

In the case of patients lost to follow-up, multiple attempts to contact the patient must be made and documented in the patient's medical records before a patient can be registered as being lost to follow-up. Multiple attempts are considered 3 telephone calls. If the patient does not respond, a letter must be sent to the patient. If no response is received a month after the letter was sent, the patient can be registered as lost to follow-up.

In general, withdrawn patients will not be replaced during the study. However, during the Safety Run-in Period in Part A, withdrawn patients will be replaced if less than 16 of the planned 24 patients complete the Day 28 Visit. In such a situation, the withdrawn patients will be replaced with an appropriate number of new patients to ensure that between 16 and 24 patients complete the Day 28 Visit of Part A (ie, complete the Safety Run-in Period).

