5.2 Rationale for Dosing

EYP001a Phase 1 data in healthy subjects showed that EYP001a was well tolerated after single and multiple oral administrations from 30 to 800 mg (single ascending dose) and from 60 to 500 mg (multiple ascending dose). For all dosing conditions, despite similar rapid EYP001a elimination, FGF19 and C4 showed a prolonged FXR target engagement up to at least 24 hours, which was not influenced by fasting or fed condition or by morning or evening administration (Study EYP001-102). EYP001a was safe in HBV subjects treated over 4 weeks with doses of EYP001a 100 mg QD, 150 mg BID, 200 mg QD, 200 mg BID, 300 mg QD, and 400 mg QD. The most frequent TEAEs were headache, pruritus, abdominal pain, and diarrhea. Pruritus was mostly seen with BID administration and was of mild or moderate intensity and lasted for 5 to 36 days. In addition, the QD doses showed better tolerance with few pruritus TEAEs.

Population PK/PD simulations for C4 and FGF19, based on preliminary modeling, support the doses and dosing regimens selected for Part A of this study: 100 mg BID versus 200 mg QD and 400 mg QD. The expected differences in C4 and FGF19 (AUC at 24 hours) at steady state between EYP001a and placebo treatments were assessed in simulations in healthy subjects and in patients with chronic HBV infection. The selected regimen and doses suggest that, in NASH patients, relevant C4 and FGF19 changes (C4 decrease and FGF19 increase) will occur. Patients with NASH were expected to have values that fell between those simulated in healthy subjects and in subjects with HBV.

The preliminary and unblinded analysis of Part A of the current study, EYP001-202, showed that EYP001a was safe in 24 male and female patients with stage F2 to F3 NASH. A higher than expected pruritus rate (60% for patients treated with the 200 mg QD dose and 83% for patients treated with the 100 mg BID and 400 mg QD doses) was observed. Patients who received 200 mg QD EYP001a interestingly reported less intense pruritus as compared to other dose groups (Figure 5, Section 1.2.2). Also, NASH subjects who early-terminated their participation due to pruritus experienced pruritus during the first week, while NASH subjects who completed their participation experienced pruritus later (Figure 6, Section 1.2.2). These observations support an EYP001a uptitration strategy to improve tolerance of pruritus.

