9.1 Adverse Events

An adverse event is defined as any untoward medical occurrence in a clinical investigation patient administered a pharmaceutical product, which does not necessarily have a causal relationship with this treatment. An adverse event can therefore be any unfavorable and/or unintended sign (including an abnormal laboratory finding), symptom, or disease temporally associated with the use of an investigational medicinal product, whether or not related to the investigational medicinal product. All adverse events, including observed or volunteered problems, complaints, or symptoms, are to be recorded on the appropriate eCRF.

Adverse events, which include clinical laboratory test variables, will be monitored and documented from the time of informed consent until the EOS Visit. Patients should be instructed to report any adverse event that they experience to the Investigator, whether or not they think the event is due to study drug. Beginning at the time of informed consent, Investigators should make an assessment for adverse events and record the event on the appropriate adverse event eCRF. Beginning with receipt of first dose of study drug, any adverse event that occurs during the Treatment Period will be recorded as a TEAE on the appropriate eCRF.

Wherever possible, a specific disease or syndrome rather than individual associated signs and symptoms should be identified by the Investigator and recorded on the eCRF. However, if an observed or reported sign or symptom is not considered a component of a specific disease or syndrome by the Investigator, it should be recorded as a separate adverse event on the eCRF. Additionally, the condition that led to a medical or surgical procedure (eg, surgery, endoscopy, tooth extraction, or transfusion) should be recorded as an adverse event, not the procedure itself.

Any medical condition already present at screening should be recorded as medical history and not be reported as an adverse event unless the medical condition or signs or symptoms present at baseline changes in severity, frequency, or seriousness at any time during the study. In this case, it should be reported as an adverse event: worsening of preexisting condition.

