9.3 Serious Adverse Event Reporting – Procedures for Investigators

Initial Reports

All SAEs occurring from the time of informed consent until 14 days following the last administration of study drug must be reported to ENYO Pharma SA (hereinafter, ENYO) and its safety designee within 24 hours of the knowledge of the occurrence.

To report the SAE, complete the SAE form electronically in the electronic data capture (EDC) system for the study and also complete and submit the SAE form to the safety vendor. When the form is completed, ENYO safety personnel and its safety designee will be notified electronically by the EDC system that an event has been added. If the event meets serious criteria and it is not possible to access the EDC system, send an email to the ENYO safety designee or call the ENYO safety designee SAE reporting line (contact information listed below), and fax/email the completed paper SAE form to the ENYO safety designee within 24 hours of awareness. When the EDC system becomes available, the SAE information must be entered within 24 hours of the system becoming available.

Follow-Up Reports

The Investigator must continue to follow the patient until the SAE has subsided or until the condition becomes chronic in nature, stabilizes (in the case of persistent impairment), or the patient dies.

Within 24 hours of receipt of follow-up information, the Investigator must update the SAE form electronically in the EDC system for the study and submit any supporting documentation (eg, patient discharge summary or autopsy reports) to the ENYO safety designee via fax or email. If it is not possible to access the EDC system, refer to the procedures outlined above for initial reporting of SAEs.

Safety Contact Information

PharmaLex

[contact]

[contact]

Email: [contact]

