APPENDIX B: CLINICAL LABORATORY ANALYTES

Serum Chemistry Panel

Alanine aminotransferase (ALT)	Gamma-glutamyl transferase
Albumin	Glucose
Alkaline phosphatase	Lactate dehydrogenase
Amylase	Potassium
Aspartate aminotransferase (AST)	Sodium
Blood urea nitrogen	Total bilirubin [1]
Calcium	Total protein
Creatine kinase (CK)	Uric acid
Creatinine	
CK-muscle/brain	
Estimation of glomerular filtration rate by the Modification of Diet in Renal Disease formula	
1. If >upper limit of normal, add conjugated (direct) bilirubin.	

Additional Chemistry Parameters

Alpha 2 macroglobulin	Ferritin
Autotoxin	Phosphate
Cardiac troponin I	

Efficacy Parameters

ALT	Adiponectin
AST	Cytokeratin-18
AST/ALT ratio	Interleukin 6
Iron-corrected T1	Fibronectin
High sensitivity C-reactive protein	Procollagen type III N-terminal peptide
Tumor necrosis factor alpha	Pro-C3
Chitinase-3-like protein 1 (also known as YKL-40)	Tissue inhibitor of metalloproteinases-1 (and derived enhanced liver fibrosis score)
Hyaluronic acid	

Pharmacodynamic Parameters

7 α hydroxy-4-cholesten-3-one	Fibroblast growth factor 19
Total bile acids	Chenodeoxycholic acid [1]
Deoxycholic acid [1]	Lithocholic acid [1]
1. Plasma levels of total, primary, and secondary bile acids may be assessed as appropriate.	

Lipid and Metabolic Profile

Branched-chain amino acid concentrations [1]

Hemoglobin A1c

Homeostatic model assessment for insulin resistance (morning fasting glucose and insulin)

Lipoprotein insulin resistance index by nuclear magnetic resonance based on serum cholesterol, high-density lipoprotein cholesterol, low-density lipoprotein (LDL) cholesterol, triglycerides, apolipoprotein B, small dense-LDL, and lipoprotein(a)

Lipoprotein particle size

Small LDL particle number

Small very low-density lipoprotein (VLDL) particle number

VLDL size

1. Liver function test.

Endocrinology

Human chorionic gonadotropin (hCG) [1]

Free triiodothyronine

Thyroid-stimulating hormone

Follicle-stimulating hormone (FSH) [2]

Free thyroxine

1. Serum hCG pregnancy test at screening and at study exit (whether at the End of Study or Early Termination Visit). Only urine hCG tests will be performed at all other study visits. If the urine hCG test is positive, pregnancy will be confirmed by a serum hCG test.
2. FSH level will be measured at screening to confirm postmenopausal state in women ≤55 years of age.

Coagulation

Activated partial thromboplastin time

Fibrinogen

International normalized ratio

Prothrombin time

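### Patients who leave before completing treatment have no scheduled contact for at least 12 of the 14 days of the SAE reporting window, and the end of their AE collection is undefined

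*Protocol*

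**What the plan says.** Protocol Section 6.5 asks a patient who leaves before completing the Treatment Period to "return to the clinic for an ET Visit within a maximum of 48 hours after their last intake of study drug". The ET footnotes of Tables 7 and 8 repeat this. Neither 6.5 nor either schedule places a visit or call after the ET Visit. An Appendix B footnote on pregnancy testing treats the EOS and ET Visits as alternative points of study exit.

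Two collection periods run past that visit. Section 9.3: "All SAEs occurring from the time of informed consent until 14 days following the last administration of study drug must be reported". Section 9.1 says that AEs "will be monitored and documented from the time of informed consent until the EOS Visit".

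Completers finish treatment on Day 84 (6.5) and attend the EOS Follow-up Visit, with AE assessment, on Day 98 (6.4). A patient who leaves between Day 84 and the EOS Visit has an ET Visit no later than the planned EOS date (6.5).

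Section 4.4 includes "Patient meeting any of the stopping rules" among the reasons for which participation may be discontinued.

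**The concern.** The protocol sets 14 days after the last dose as its SAE window, and its visit plan meets that window only for patients who finish treatment. For early leavers the window has no scheduled check, and 9.1 ties the end of AE collection to a visit that is not on their path.

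Early leaving is likely to be related to tolerability. In Part A, investigator-reported pruritus occurred in 60% to 83% of patients across the active groups and in none on placebo (Protocol 1.2.2). The SAP counts as treatment-emergent any AE starting on or after the first dose, with no limit after the last dose, and reports numbers and percentages of patients by arm (SAP 3.7.1). A completer's event on Days 85 to 98 is asked about at a visit and counted. The same event in an early leaver is counted only if someone reports it. If more patients leave the active arms, their post-drug events would be under-counted relative to placebo. Safety is part of the primary objective (Protocol 2.1).

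**Working it through.** **1. Number of early leavers in the plan.** Inputs from Protocol 10.2.8: difference 5.1, SD 5.8, one-sided alpha 0.0125, power 0.8.

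- n per arm = 2 × [SD × (z for alpha + z for power) / difference]² = 2 × [5.8 × (2.241 + 0.842) / 5.1]² = 24.6, so 25 with a Z-test.
- The stated 26 is what the t-test version gives: power is 0.784 at 25 and 0.802 at 26.
- Allowing for dropout: 26 / (1 − 0.13) = 29.9, so 30.

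The stated 26 and 30 are reproduced for practical purposes. They imply 30 − 26 = 4 leavers per arm, or 90 − 3 × 26 = 12 of 90 (directly, 0.13 × 90 = 11.7).

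**2. Days without scheduled contact, per patient.**

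| | Last scheduled AE assessment | Days of the 14 without scheduled coverage |
|---|---|---|
| Completer | Day 98, and 98 − 84 = 14 days after last dose | 0 |
| Leaver before completing treatment | 0 to 2 days after last dose | 14 − 2 = 12 (86%) to 14 − 0 = 14 (100%) |

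**3. Part B as a whole.** Post-drug patient-days at 14 per patient: 90 × 14 = 1,260. Without scheduled coverage: at least 12 × 12 = 144, and 144 / 1,260 = 11.4%.

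**4. Balance between arms.** The documents do not say how dropout will divide, so two cases are shown as assumptions.

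- Equal dropout: 26 / 30 = 87% of each arm has the full 14-day check.
- All 12 leavers on active drug, 6 per arm: 30 / 30 = 100% on placebo against 24 / 30 = 80% on each active arm.

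**5. Chance that an SAE begins in the uncovered days.** The documents give no SAE risk. Assume a risk r per leaver, spread evenly over the 14 days. For 12 leavers the chance of at least one is 1 − (1 − r × 12/14)^12: 19% at r = 2%, 41% at 5% and 66% at 10%. This is the chance that an event begins, not that it goes unreported.

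**6. Whether other provisions cover the gap.**

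| Provision | What starts it | Looks for new events after the ET Visit? |
|---|---|---|
| Liver follow-up to resolution, close observation (Appendix E) | Known liver abnormality | No |
| Weekly monitoring after a muscle/CK stop (Appendix E) | Known muscle or cardiac finding | No |
| SAE follow-up to outcome (9.3) | Known SAE | No |
| Laboratory follow-up to normal or stable (9.1) | Known significant abnormality | No |
| Patients told to report AEs (9.1) | Patient's initiative | Passive only |

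None of these records the outcome of a non-serious symptom, such as pruritus or nausea, that is still present at the ET Visit.

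**The case against.** The case against rests on safeguards, scope and size.

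**Safeguards.** A reader might infer that early leavers have no later contact, that the SAE window is never checked, or that post-drug AEs are collected only in completers. The documents support none of these. The event-triggered provisions above apply to non-completers, the 14-day SAE duty and passive reporting remain, and the ET Visit itself assesses AEs, chemistry and ECG. Patients who leave after Day 84 may be seen as late as the planned EOS date.

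**Scope.** Stopping drug is not clearly the same as leaving the study. Section 3.2 says that dosing may be discontinued and allows reinitiation, and 4.4 says that participation may be discontinued. A patient who stops drug for safety could stay in and reach Day 98. The gap is established only for those who leave.

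**Part A evidence.** Three inferences are tempting and should not be drawn.

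- The pruritus that "was of mild or moderate intensity and lasted for 5 to 36 days" (5.2) was seen in HBV patients, mostly with BID dosing. It is an event duration, not persistence after the last dose, and Part B is NASH with QD dosing.
- The 19 patients who had completed Week 4 at the first interim (SAP 4.1) do not show that the other 5 of 24 dropped out. The SAP does not say why they are not counted.
- The pruritus contrast is by investigator report. On the visual analog scale 4 of 7 placebo patients also reported it (1.2.2). Part B also drops two Part A regimens and adds uptitration, so Part A rates may not carry over.

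**Size.** Pruritus that begins in the first week on drug is already captured by the ET Visit. Safety summaries are descriptive, so no test depends on this interval. Against all planned Part B days, 90 × 98 = 8,820, the gap is 144 / 8,820 = 1.6%.

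All of this limits the claim, but it does not supply a scheduled check or an AE end point for early leavers. The 1.6% is mostly time on drug. For post-drug safety the relevant denominator is post-drug time, where the share is 11.4%.

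**Conclusion.** The point holds in limited form. Sections 6.5, 9.1 and 9.3 do not fit together for a patient who leaves before completing treatment: scheduled assessment stops within 48 hours of the last dose, SAEs are reportable for 14 days, and AE collection has no stated end.

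The size rests on the protocol's 13% dropout and on each leaver attending the ET Visit in time: about 12 of 90 Part B patients, each with 12 or more of the 14 days not covered. A difference between arms is conditional on unequal dropout, which Part A makes plausible but does not establish for Part B. The sample size, alpha, power and LFC analysis are not affected. This is a worthwhile and cheap correction to data collection, not a flaw that threatens the trial's main result.

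**What to change.** Reconcile Sections 6.5, 9.1 and 9.3 of the Protocol:

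- In 6.5 and the ET footnotes of Tables 7 and 8, add one safety contact 14 days after the last dose for every ET patient who has not withdrawn consent to contact. A telephone call is enough. It should record new AEs and SAEs, the outcome of ongoing events and concomitant medication.
- In 9.1, state that AE collection ends 14 days after the last dose for all patients. For a completer whose last dose is on Day 84 this is Day 98, as now.

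This uses the protocol's own window and changes data collection only. For patients who are reached, scheduled coverage rises from at most 2 of 14 days to 14 of 14. If all are reached, the Part B shortfall falls from at least 144 patient-days to 0. The cost is protocol wording and about 12 calls at the planned dropout. Some withdrawn patients will decline, so part of the gap will remain.
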